## 2.10 Scientific and Clinical Justification of the Protocol

The current management of MDS is suboptimal. Current therapies include hypomethylating agents, lenalidomide and immunosuppressive therapy. None of these are curative and remissions are short-lived. Patients with MDS relapsed or refractory to standard therapy, and not eligible or suitable for allogeneic stem cell transplantation receive supportive care with transfusions and antibiotics in the setting of infection. Quality of life is severely impacted by the necessity to come to a treatment center as frequently as several times every week to receive transfusions. Thus, decreasing or abrogating the need for transfusions could significantly improve the quality of life and ability to carry out normal daily activities. New treatment modalities are needed for this population.

Thrombopoietin (TPO) is a potent endogenous cytokine and the principal regulator of platelet production. On binding to TPO receptors on megakaryocyte progenitors, TPO initiates a number of signal transduction events to increase the production of mature megakaryocytes and platelets. The non-peptide mimetic eltrombopag, a 2nd generation TPO-agonist, has been shown to increase platelets in healthy subjects and in patients with chronic immune thrombocytopenic purpura (ITP). Eltrombopag is administered orally, well tolerated and does not induce auto-antibodies, in contrast to first-generation TPO-R agonists such as megakaryocyte growth and development factor.

In efficacy studies in subjects with ITP, more than 59% of subjects responded with a clinically meaningful increase in platelet counts, regardless of baseline platelet counts, use of concomitant medication and/or splenectomy status. Eltrombopag induced elevations in platelet counts  $\geq 50$  K/ $\mu$ L. Clinically significant bleeding (WHO Bleeding Grades 2 to 4) in the eltrombopag 50 mg treatment groups was nearly one-half that observed in the placebo–treatment groups. Summary data indicate in the 269 subjects with ITP who received at least one dose of eltrombopag (from 30 to 75 mg) in either a short-term study (Studies TRA100773A and TRA100773B) for up to 6 weeks or an ongoing open-label study (Studies TRA105325/EXTEND and TRA108057/REPEAT): A dose-dependent increase in platelet count was observed after 5 to 10 day repeat dosing with eltrombopag. Maximum platelet counts were observed approximately 2 weeks after initiating dosing, and returned to within normal limits within 2 weeks after discontinuation of eltrombopag dosing in healthy adult subjects. Transient decreases in platelet counts to levels below baseline were observed in subjects after eltrombopag treatment cycles in REPEAT. However, the decreases in platelet count were not accompanied by clinically meaningful increases in bleeding symptoms. Consistent response to eltrombopag was observed based upon analysis of the primary endpoint in the REPEAT study. Eighty-eight percent of subjects who responded in Cycle 1, responded again in Cycle 2 or 3, with a similar pharmacodynamic response to eltrombopag and a decrease in bleeding symptoms as observed in Studies TRA100773A and TRA100773B. Efficacy data from the EXTEND study show clinically meaningful continuous platelet count elevations  $\geq 50,000/\mu$ L for at least 10 consecutive weeks in the majority of subjects, with 24% achieving continuous elevation of platelet counts  $>50,000/\mu$ L for more than 6 months and a decrease in bleeding symptoms.

Because, severe dysfunction of megakaryocytes is the cause of thrombocytopenia in MDS patients, and because of the efficacy demonstrated in ongoing ITP clinical trials and subsequent FDA approval for use in ITP, we now propose this Phase 2, non-randomized pilot study of eltrombopag in patients with MDS. We hypothesize that the drug will stimulate more robust platelet production from the dysplastic megakaryocyte pool, and also potentially help drive primitive hematopoietic stem and progenitor cells to produce more megakaryocytes. In addition, this agent is likely to produce trilineage responses as it acts at the level of the hematopoietic stem cell. Ancillary studies will address questions such as identification of clinical and laboratory predictors of response, as well as cellular and molecular mechanism of eltrombopag action and the mechanism by which

[figure not shown]
megakaryocyte function is impaired in MDS.

We therefore propose this non-randomized, pilot, phase II study of eltrombopag in low to Int-2 risk MDS patients with cytopenias that persists despite treatment with standard therapies to assess its effectiveness in this population.

### 3. STUDY DESIGN

The study is designed as a non-randomized, Phase II, dose modification study of the oral TPO-R agonist eltrombopag in subjects with MDS with any cytopenia. The primary endpoint is measured at 16 or 20 weeks. Subjects who cannot tolerate the medication or fail to respond will go off study medication. In the event that a subject is transfused platelets for a count  $>10,000/\mu\text{L}$  without a medical indication during the study period, the subject may continue on study drug and the response assessment may be extended for an additional 4 weeks at the discretion of the principal investigator to ensure eligibility to enter the extended access portion of the trial. Subjects with evidence for a clinical response in any lineage at 16 weeks but not yet meeting full primary endpoint response criteria, and who are tolerating investigational treatment, may receive an additional 4 weeks of eltrombopag and be reassessed after 20 weeks. At that time, if they meet primary endpoint response criteria, they will be eligible to enter the extended access part of the study. If they do not meet primary endpoint response criteria, eltrombopag will be discontinued.

Subjects with response may continue study medication (extended access) at the lowest dosage that maintains stable counts or taken off drug for robust response until they meet off study criteria. If subjects are taken off drug for robust response and maintain response, they will be taken off study after 2 years.

### 4. ELIGIBILITY ASSESSMENT

#### 4.1 Inclusion criteria

- 4.1.1 Diagnosis of MDS, with WHO classification of refractory anemia, refractory cytopenia with unilineage dysplasia (RCUD), RARS, RCMD-RS, or RCMD
- 4.1.2 IPSS risk scores of low, intermediate-1, or intermediate-2.
- 4.1.3 Platelet count  $\leq 30,000/\mu\text{L}$  or platelet-transfusion-dependence (requiring at least 4 platelet transfusions in the 8 weeks prior to study entry); OR hemoglobin less than 9.0 gr/dL or red cell

- transfusion-dependence (requiring at least 4 units of PRBCs in the eight weeks prior to study entry) OR ANC $\leq$ 500
- 4.1.4 Age  $\geq$  18 years old
  - 4.1.5 Treatment naïve or off all other treatments for MDS (except stable dosing of filgrastim (G-CSF), erythropoietin, and transfusion support) for at least four weeks. G-CSF can be used before, during and after the protocol treatment for subjects with documented neutropenia (<500/UL) as long as they meet the criteria for other cytopenias as stated above. G-CSF must be held for 3 weeks prior to enrollment bone marrow biopsy and prior to each study assessment bone marrow biopsy, unless clinically indicated to avoid infections per PI discretion.
  - 4.1.6 Adequate liver function, as evidenced by total serum bilirubin  $\leq$  1.5 times the upper limit of normal (patients with Gilbert's disease are eligible, provided intermittent indirect hyperbilirubinemia, AST or ALT  $\leq$  5 times the upper limit of normal).
  - 4.1.7 A serum creatinine concentration  $\leq$  2 x ULN

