## 4.2 Exclusion criteria

- 4.2.1 WHO classification of chronic myelomonocytic leukemia (CMML), RAEB-1, RAEB-2, AML
- 4.2.2 Treatment with horse or rabbit ATG or Campath within 6 months of study entry
- 4.2.3 Subjects with liver cirrhosis including subjects infected with Hepatitis B or C
- 4.2.4 Subjects with HIV
- 4.2.5 Infection not adequately responding to appropriate therapy
- 4.2.6 History of malignancy treated with chemotherapy and cytogenetic abnormalities suggestive of secondary myelodysplasia.
- 4.2.7 Moribund status or concurrent hepatic, renal, neurologic, pulmonary, infectious, or metabolic disease of such severity that it would preclude the patient's ability to tolerate protocol therapy
- 4.2.8 Life expectancy of less than 3 months
- 4.2.9 Hypersensitivity to eltrombopag or its components
- 4.2.10 Female subjects who are nursing or pregnant or are unwilling to take oral contraceptives or refrain from pregnancy if of childbearing potential
- 4.2.11 Unable to understand the investigational nature of the study or give informed consent or does not have a legally authorized representative or surrogate that can provide informed consent per section 10.5

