### 5.3 Dose delays, modifications or discontinuation for non-hematologic side effects

**5.3.1 Infection:** Subjects who experience an infection requiring intravenous antibiotics will not have eltrombopag discontinued. If the subject experiences infection severe enough to require vasopressors or intubation, the drug will be withheld until the subject is stable.

**5.3.2 Liver function abnormalities:** In the event of an increase in the ALT level to > 6 times the ULN, -subjects will return to clinic or have blood tests drawn by their home physician every 3-4 days. If the ALT remains > 6 times the ULN on a second blood test, eltrombopag will be discontinued until ALT is < 5 times the ULN. Eltrombopag will be restarted at a dose level 25mg/day lower than the prior dose. If the toxicity appeared on a dose of 25 mg/day, eltrombopag will be discontinued permanently. If liver tests abnormalities return to and ALT of > 6 times ULN on this reduced dose, eltrombopag will be permanently discontinued.

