## 6. CLINICAL MONITORING

### 6.1 Pre-study Evaluation

Patients will be screened for participation by signing consent to participate in a NHLBI screening protocol. Their eligibility to participate in this protocol will be determined based on the Inclusion and Exclusion criteria (Section 4) and data collected on the screening protocol. The time between determination of eligibility for this protocol and signing informed consent for this protocol should be 4 weeks or less.

Baseline status will be evaluated as follows:

- Medical History and physical examination
- Concurrent medication review
- Baseline assessments (done at screening or diagnostic workup, not repeated on study)
  - Folate level
  - B12 level
  - Iron panel (ferritin, transferrin, % saturation)
- Baseline laboratory studies (evaluations designated with an \* must be repeated within 72 hours of the first dose of study drug, all others within 6 months of study entry)
  - Complete blood count with differential\*
  - Reticulocyte count\*
  - Acute care, mineral and hepatic panels, CK, LDH, total protein and uric acid\*
  - Pregnancy test (urine or blood HCG in women of child bearing potential)\*
  - Thyroid function tests
  - Peripheral blood smear
  - Viral serologies for HIV, hepatitis B, C, HSV, EBV and CMV
  - HLA typing (if not already available)
  - DAT (direct antiglobulin test)
  - Type and screen (as clinically indicated)

Flow cytometry of the peripheral blood for GPI-cells  
Lymphocyte phenotyping (TBNK flow cytometry)

- Bone marrow aspirate and biopsy with reticulin and collagen fiber staining and cytogenetic analysis (morphology, cellularity, percentage of blast cells on aspirate), flow cytometry (at clinician discretion,) within four months of first dose of study drug

## 6.2 Monitoring study drug initiation through Week 16 or 20

Subjects will be monitored weekly as long as they remain on study drug through week 16. At a minimum, subjects must be evaluated at the NIH Clinical Center at week 16 (+/- 4 days). If subjects are kept on drug an additional 4 weeks to assess response, they must be evaluated at the NIH clinical center at week 20 (+/- 4 days). \*The week 20 evaluations will only need to be completed for subjects that are kept on drug an additional 4 weeks after week 16 to assess response.

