Subjects must have weekly blood tests at the NIH or drawn by their referring health care provider. If subjects are to be followed at home for interim visits, progress notes and laboratory results from their health care provider and laboratory must be faxed to the study research nurse, at [name]. The following assessments will be done:

- Clinical assessment (weeks 4, 8, 12, 16, and 20\* +/- 4 days, if seen at the NIH CC only)
- Concurrent medication review (with each clinical assessment)
- CBC with differential (weekly +/- 4 days)
- Acute care, mineral and hepatic panels, CK, LDH, total protein and uric acid (weekly +/- 4 days) (Home MDs: electrolytes, transaminases, urea nitrogen (BUN), serum creatinine clearance, total bilirubin)
- Reticulocyte count (weekly +/- 4 days) (If seen at home, only if available)
- DAT (direct antiglobulin test) (as clinically indicated)
- Type and screen (as clinically indicated)
- Pregnancy test (urine or blood HCG) in woman of childbearing potential (4, 8, 12, 16, and 20\* weeks +/- 4 days)
- Bone marrow aspirate and biopsy with reticulin and collagen fiber staining and cytogenetic analysis at primary end point (morphology, cellularity, percentage of blast cells, and/or chromosomal analysis by PCR) (week 16 +/- 4 days or if clinical indicated)
- Flow cytometry of bone marrow aspirate (week 16 and 20\* +/- 4 days) (at clinician discretion)
- Flow cytometry of the peripheral blood for GPI-cells
- Lymphocyte phenotyping (TBNK flow cytometry 16 and 20\* weeks +/- 4 days)

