**For subjects with hepatic impairment:** The pharmacokinetics of eltrombopag has been studied after administration of eltrombopag to adult patients with hepatic impairment. Following the administration of a single 50 mg dose, the AUC0-∞ of eltrombopag was increased by 41% in subjects with mild hepatic impairment and by 80% to 90% in subjects with moderate or severe hepatic impairment compared with healthy volunteers. Therefore, patients with minimally impaired hepatic function will be included but participation will be monitored closely.

**For pregnant and nursing mothers:** Eltrombopag was not teratogenic when studied in pregnant rats and rabbits but caused a low incidence of cervical ribs (a fetal variation) and reduced fetal body weight at doses that were maternally toxic. There are no adequate and well-controlled studies of eltrombopag in pregnant women. The effect of eltrombopag on human pregnancy is unknown. Therefore, women of childbearing potential must agree to use adequate contraception prior to (hormonal or barrier method of birth control; abstinence) and for the duration of study participation. If a woman becomes pregnant or suspects she is pregnant while on study, her treating physician should be informed immediately.

**Recruitment efforts:** The study will be listed on the [clinicaltrials.gov](http://clinicaltrials.gov), Clinical Center research studies, The MDS Foundation, and the National Heart, Lung and Blood Institute patient recruitment websites. If recruitment goals are not met, recruitment plan will be developed by the Clinical Center Office of Patient Recruitment. Hematologists and Oncologists throughout the country will be informed about the protocol by letter.

**Competition between Branch Protocols:** There are no competing Branch protocols for this patient population. The ability to offer patients who fail to have an optimal response to initial immunosuppression protocols another option will be a very positive addition to our MDS program.

**Reimbursement for protocol, travel, food, and lodging** will be consistent with NHLBI DIR Travel and Lodging Compensation of Clinical Research Subjects policy or institutional guidelines.

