### RISK OF HEPATOTOXICITY

See full prescribing information for complete boxed warning.

In patients with chronic hepatitis C, PROMACTA in combination with interferon and ribavirin may increase the risk of hepatic decompensation.

**PROMACTA may increase the risk of severe and potentially life-threatening hepatotoxicity. Monitor hepatic function and discontinue dosing as recommended.**

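### Criterion 4.1.6 puts the AST/ALT limit inside the Gilbert's parenthesis, so a subject without Gilbert's disease and with bilirubin at or below 1.5 × ULN has no numeric transaminase limit at entry

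*Combined protocol and SAP*

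**What the plan says.** Section 4.1.6 asks for adequate liver function, shown by total bilirubin at or below 1.5 × ULN. One parenthesis follows: "patients with Gilbert's disease are eligible, provided intermittent indirect hyperbilirubinemia, AST or ALT" no more than 5 × ULN. It closes after that enzyme limit, and nothing else in 4.1.6 mentions AST or ALT.

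Section 5.3.2 governs ALT on treatment. It begins "In the event of an increase in the ALT level to > 6 times the ULN" and calls for blood tests every 3 to 4 days. If a second test is still above 6 × ULN, "eltrombopag will be discontinued until ALT is < 5 times the ULN", and drug then resumes at a dose 25 mg/day lower. None of this depends on Gilbert's status.

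Section 6.1 lists the hepatic panel among the baseline tests that "must be repeated within 72 hours of the first dose of study drug". It attaches no threshold, and it determines eligibility from the criteria in section 4 and the screening-protocol data. Section 10.1 says that "patients with minimally impaired hepatic function will be included but participation will be monitored closely". The boxed warning reproduced in section 10.3.1 states that "PROMACTA may increase the risk of severe and potentially life-threatening hepatotoxicity".

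**The concern.** Section 4.1.6 is the only numeric liver gate at entry, and the drug carries a boxed hepatotoxicity warning. With the bracket where it is, the enzyme limit covers only the subjects to whom the Gilbert's allowance applies. For everyone else, the pre-dose hepatic panel is measured but the text gives no AST or ALT number to compare it with.

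The result is also inconsistent with the protocol's own treatment rule. A subject can be started at an ALT at which the same protocol would refuse to restart. At stake are subject safety and uniform application of an eligibility threshold. The efficacy test is not at stake.

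**Working it through.** No figure in the plan is to be reproduced. The check is a reading of 4.1.6 against every other liver statement.

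**1. Parse of 4.1.6.** The main clause is bilirubin ≤ 1.5 × ULN. The parenthesis contains the Gilbert's allowance and its conditions, and AST or ALT ≤ 5 × ULN is one of those conditions. A subject without Gilbert's disease, with bilirubin 1.0 × ULN and ALT 8 × ULN (values chosen for illustration), satisfies the main clause and is not reached by the parenthesis. That subject meets the numeric part of 4.1.6.

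**2. Search for a numeric AST/ALT limit at entry elsewhere.**

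| Section | Content | Numeric AST/ALT entry limit? |
|---|---|---|
| 4.2.3 | Excludes cirrhosis and hepatitis B or C | No, by diagnosis |
| 4.2.7 | Excludes concurrent disease, hepatic included, too severe to tolerate therapy | No, by judgement |
| 6.1 | Hepatic panel before the first dose | No threshold |
| 10.1 | Describes minimal hepatic impairment as acceptable | No |
| 5.3.2 | ALT > 6 × ULN, restart at < 5 × ULN | No, on treatment |
| 10.3.1.2 | Label discontinuation levels | No, on treatment |

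By contrast, 4.1.7 gives creatinine its own numeric criterion.

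**3. Comparison with 5.3.2.** Restart requires ALT < 5 × ULN for all subjects. Entry, for the subject in step 1, has no number. So 8 × ULN is admissible at entry, is above the action level (8 > 6), and would bar a restart (8 ≥ 5). The restart level nearly matches the limit in the parenthesis, which suggests that 5 × ULN was meant for everyone.

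**4. What 5.3.2 would do after entry.** Assume same-day results and that the rule applies to a subject already raised at baseline.
- If the first weekly panel under 6.2 is the first test: day 7 ± 4 gives day 3 to 11. The second test is 3 to 4 days later, so the stop falls at day 3 + 3 = 6 to day 11 + 4 = 15.
- If the pre-dose panel (day −3 to 0) counts as the first test: the second falls at day −3 + 3 = 0 to day 0 + 4 = 4.

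The second assumption is not secure, because 5.3.2 is triggered by an increase to above 6 × ULN and does not say whether a baseline value already above it counts. Section 5.3.2 also names ALT only and sets no action level for AST.

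**5. A smaller ambiguity.** The words linking AST and ALT can be read as satisfied by either enzyme alone. Under that reading, a Gilbert's subject with bilirubin above 1.5 × ULN could pass with only one enzyme within limits.

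**The case against.** The strongest reply is that this is an editorial slip which no investigator would exploit. The controlling words of 4.1.6 are adequate liver function. Enrolling a subject with ALT well above 6 × ULN would mean calling that adequate, setting aside 10.1, and disregarding the only enzyme number in the criterion. Section 4.2.3 removes cirrhosis and viral hepatitis, with serologies in 6.1. Section 4.2.7 removes anyone with "metabolic disease of such severity that it would preclude the patient's ability to tolerate protocol therapy", and its list includes hepatic disease. After entry there are weekly panels, the 5.3.2 stop, a dose-reduced restart and permanent discontinuation on recurrence, and 8.6 takes persistent hepatotoxicity off drug. All of this stands, and it limits the practical effect. None of it supplies a number at entry, so the threshold depends on how each reader repairs the sentence.

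A reader might infer that Gilbert's subjects with bilirubin within the limit are equally unprotected. The documents do not settle this. Such a subject meets the main clause, but the proviso can also be read as binding every Gilbert's patient whatever the bilirubin. The firm claim therefore covers subjects without Gilbert's disease.

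**Conclusion.** The point holds as a wording error in an operative eligibility threshold. As written, a subject without Gilbert's disease and with bilirubin at or below 1.5 × ULN has no numeric AST or ALT limit at entry, and could start drug above the 6 × ULN action level. A Gilbert's subject with bilirubin in that range arguably has none either.

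It rests on a literal reading of the parenthesis; the probable intent is 5 × ULN for all. How many subjects it could affect cannot be stated, because the documents give no rate of raised transaminases in this population, and it may be rare. Sample size, alpha and power are unaffected.

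A reader might go further and infer that the protocol leaves the liver unguarded, or that subjects were in fact enrolled with high ALT. The documents support neither: the safeguards are real, though non-numeric or later, and nothing reports such an enrollment. The correction is worth making because it restores the evident intent at almost no cost.

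**What to change.** Close the parenthesis after the condition on intermittent indirect hyperbilirubinemia, and split 4.1.6 in two:
- (a) total bilirubin ≤ 1.5 × ULN, with the Gilbert's allowance as now;
- (b) for every subject, AST and ALT each ≤ 5 × ULN.

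Requiring each enzyme also removes the either-one reading.

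State that (b) is checked on the hepatic panel repeated within 72 hours of the first dose. This matters because 6.1 determines eligibility from screening data and allows up to 4 weeks between that determination and consent, so ALT could rise in the interval. Only if the 72-hour panel is the qualifying one can the protocol claim that each subject's last pre-dose ALT is below the 6 × ULN action level.

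The cost is a one-line amendment, no new test, and a rare extra screen failure.
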